8.5. Reporting Adverse Events

All SAEs (related and unrelated) will be recorded from the first administration of study drug until the Follow-Up visit. All SAEs discovered by the Investigator at any time should be reported. All SAEs must be reported to SiteOne Therapeutics, Inc. within one business day of the first awareness of the event. The Investigator must complete, sign and date the SAE pages, verify the accuracy of the information recorded on the SAE pages with the corresponding source documents, and send a copy by telephone or email to SiteOne Therapeutics, Inc.

Additional follow-up information, if required or available, should all be emailed to SiteOne Therapeutics, Inc. within one business day of receipt and this should be completed on a follow-up SAE form and placed with the original SAE information and kept with the appropriate section of the CRF and/or study file.

SiteOne Therapeutics, Inc. is responsible for notifying the relevant regulatory authorities of certain events. It is the Principal Investigator's responsibility to notify the IRB or IEC of all SAEs that occur at his or her site. Investigators will also be notified of all unexpected, serious, drug-related events (7/15 Day Safety Reports) that occur during the clinical trial. Each site is responsible for notifying its IRB or IEC of these additional SAEs.

9. **STATISTICS**

9.1. Statistical Methods

Treatment effects on safety and tolerability will be evaluated using descriptive statistics (mean, standard deviation, median, minimum, maximum) of the number and proportion of subject experiencing adverse events by system organ class, and preferred term.

Prior to dosing on Day 1, three separate measurements of supine blood pressure (BP; diastolic blood pressure [DBP], systolic blood pressure [SBP]) and heart rate (HR) will be recorded one minute apart. These values will be averaged and used to establish the baseline from which analyses of change from baseline will be computed.

For purposes of monitoring safety, AEs will be graded using the *Toxicity Grading Scale for Healthy* Adult and Adolescent Volunteers (FDA, 2007) which is appropriate for healthy subjects.

Descriptive statistics will be used to evaluate the treatment effects on clinical laboratory assessments including clinical chemistry, hematology, and urinalysis.

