In all cohorts, study drug (ST-2427 or placebo) will be infused via IV over 1 hour. Subjects will be randomized 4:2 to receive a single dose of ST-2427 or placebo.

Subjects randomized to ST-2427 in Cohort 1 will receive 5 mg ST-2427 as a single IV infusion over one hour. The starting dose of 5 mg will be administered to all subjects in Cohort 1 regardless of body weight.

The doses of ST-2427 to be administered in all cohorts after Cohort 1 will be approved by the DMC following examination of all available clinical and PK data. In the SAD, the dose increase of

ST-2427 from Cohort 1 onwards is <2-fold from the prior cohort,

In all cohorts, placebo will be administered as 1-hour IV infusions at matching volumes and times to those administered to subjects randomized to ST-2427 in the same cohort.

Details of study drug preparation are provided in the Pharmacy Manual for this study.

Duration of Treatment:

Single 1-hour IV infusion

Reference Therapy, Dosage, and Mode of Administration:

Placebo (5% Dextrose Injection, USP) will be administered by 1-hour IV infusions at the same volume and rate as used for ST-2427

Criteria for Evaluation:

Safety:

Safety measures include incidence and severity of AE's, physical examination

body weight, ECG, clinical laboratory testing (chemistry, hematology, urinalysis), respiratory rate, body temperature, oxygen saturation, local (injection site) irritation, and QTcF measures.

Pharmacokinetics:

Blood and urine samples will be collected at specified times during the study for measurement of ST-2427 concentration using a validated analytical method. The measured concentrations will be used for PK modeling.

Statistical Methods:

Treatment effects on safety and tolerability will be evaluated using descriptive statistics (mean, standard deviation, median, minimum, maximum) of the number and proportion of subject experiencing adverse events by system organ class, and preferred term.

Prior to dosing on Day 1, three separate measurements of supine BP (including DBP, SBP) and HR will be recorded one minute apart after at least 5 minutes rest. These repeat assessments will be used for analyses of change from baseline for these measures.

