Cardiodynamic evaluation will be performed to evaluate the treatment effects on heart rate-corrected QT interval using the Fridericia (QTcF) corrections, using concentration-QTc analysis, and on other ECG parameters (heart rate, PR and QRS interval and treatment emergent T and U-wave abnormalities). The statistical analysis will be detailed in a separate SAP.

For purposes of monitoring safety, treatment-emergent adverse events (AEs) will be graded using the Toxicity Grading Scale for Healthy Adult and Adolescent Volunteers (FDA 2007) which is appropriate for healthy subjects.

Descriptive statistics will be used to evaluate the treatment effects on clinical laboratory assessments including clinical chemistry, hematology, and urinalysis.

PK modeling will be performed using compartmental methods. PK parameters such as, but not limited to C_{max} , T_{max} , Volume of distribution, Elimination half-life, and AUC after the ST-2427 infusion in the SAD. Descriptive statistics will be used to summarize PK parameters, and ST-2427

Confidential and Proprietary

concentrations in the urine by cohort. In addition, exploratory analyses of the effects of some baseline characteristics (e.g., sex, body weight) on PK parameters may be undertaken.

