3.3. Treatment Assignment

Subjects who meet all criteria for enrollment will be randomly assigned to 1 of 2 treatment groups, ST-2427 or placebo, following a 4:2 allocation. A randomization schedule will be produced by an unblinded statistician using a validated computer program. Once baseline data (Day –1) has been reviewed and subjects are determined to be eligible for the study, they will be assigned a unique randomization number. Investigators and subjects will remain blinded to the study drug assignment and only certain designated staff (such as pharmacy personnel) will be unblinded to study treatment.

Sealed code break envelopes will be provided by an unblinded statistician prior to the start of the study. During the study, the blind is to be broken by an Investigator only when subject safety is at risk and unblinding must occur to determine effective medical intervention for the subject. All unscheduled unblinding events must be reported to the medical monitor and SiteOne Therapeutics, Inc. as soon as possible.

[figure not shown]

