8.2. Adverse and Serious Adverse Events

8.2.1. Definition of Adverse Events

8.2.1.1. Adverse Event (AE)

An AE is the development of an undesirable sign (including an abnormal laboratory finding), symptom, medical condition or the deterioration of a pre-existing medical condition following or during exposure to a pharmaceutical product, whether or not considered casually related to the product. In clinical studies, an AE can include an undesirable medical condition occurring at any time, including baseline or washout periods, even if no study treatment has been administered.

It is the responsibility of the investigator to document all AEs that occur during the study. All AEs that occur after any patient/subject has been enrolled, before treatment, during treatment, or at any time up to the Follow-Up visit, whether or not they are related to the study, must be recorded on the appropriate case report forms (CRFs).

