8.2.1.3. Other Adverse Events

Other AEs will be identified by the Drug Safety Investigator and if applicable also by the Clinical Study Team Investigator during the evaluation of safety data for the Clinical Study Report. Significant AEs of particular clinical importance, other than SAEs and those AEs leading to discontinuation of the patient/subject from the study, will be classified as other AEs. For other AEs, a narrative may be written and included in the Clinical Study Report.

8.3. **Relationship to Study Drug**

An Investigator who is qualified in medicine must make the determination of relationship to the investigational product for each AE (Unrelated, Possibly Related, or Probably Related). The Investigator should decide whether, in his or her medical judgment, there is a reasonable possibility that the event may have been caused by the investigational product. If no valid reason exists for suggesting a relationship, then the AE should be classified as "unrelated." If there is any valid reason, even if undetermined, for suspecting a possible cause-and-effect relationship between the investigational product and the occurrence of the AE, then the AE should be considered "related."

If the relationship between the AE/SAE and the investigational product is determined to be "possible" or "probable" the event will be considered related to the investigational product for the purposes of expedited regulatory reporting.

8.4. **Recording Adverse Events**

AEs spontaneously reported by the patient/subject and/or in response to an open question from the study personnel or revealed by observation will be recorded during the study at the investigational site. Clinically significant changes in laboratory values, blood pressure, and pulse need not be reported as AEs. However, abnormal values that constitute an SAE or lead to discontinuation of administration of study drug must be reported and recorded as an AE. Information about AEs will be collected from the Screening at enrollment until the end of the study. SAE information will be collected from the first administration of study drug until the Follow-up visit. The AE term should be reported in standard medical terminology when possible. For each AE, the investigator will evaluate and report the onset (date and time), resolution (date and time), intensity, causality, action taken, serious outcome (if applicable), and whether or not it caused the patient to discontinue the study.

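### Could adverse events that start before the infusion be counted as treatment effects in the section 9.1 incidence tables?

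*Combined protocol and SAP*

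**What the plan says.** The synopsis and section 9.1 share the same opening: "Treatment effects on safety and tolerability will be evaluated using descriptive statistics". The statistics named are those "of the number and proportion of subject experiencing adverse events by system organ class, and preferred term". Neither place limits the events by time of onset.

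Section 8.2.1.1 starts with a definition tied to exposure, "following or during exposure to a pharmaceutical product". It then widens this for clinical studies to a condition "occurring at any time, including baseline or washout periods, even if no study treatment has been administered". The investigator must record all AEs "that occur after any patient/subject has been enrolled, before treatment, during treatment, or at any time up to the Follow-Up visit". Section 8.4 describes the start of collection differently: "Information about AEs will be collected from the Screening at enrollment until the end of the study". It also asks for date and time of onset, intensity and causality for every event.

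For adverse events, the term treatment-emergent occurs once, in the synopsis: "treatment-emergent adverse events (AEs) will be graded using the Toxicity Grading Scale". The matching sentence in section 9.1 drops the qualifier. The only other uses concern T- and U-wave findings, in the synopsis and section 9.3. Section 9.4 limits the safety population to dosed subjects, which selects people and not events. The separate SAP is announced for the ECG analysis only.

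On timing, section 3.3 says that once Day -1 baseline data "has been reviewed and subjects are determined to be eligible for the study, they will be assigned a unique randomization number". Table 4 places randomisation on Day -1.

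**The concern.** Safety and tolerability form the primary objective, and AE incidence by system organ class and preferred term is its main summary. If events that began before the infusion enter that table, part of what is labelled a treatment effect cannot be one. The protocol invites the question: it says that pre-dose events are AEs, requires them to be recorded, and then tabulates AEs without qualification. The population definition does not remove them, and no general SAP is announced that would. Two programmers working from the text alone could build different tables.

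The groups are also small. Section 6.5 gives 4 ST-2427 subjects per cohort, and section 9.6 gives 20 on ST-2427 and 10 on placebo overall. One miscounted subject would show: 1/4 = 25 points in a dose group, 1/20 = 5 points in pooled ST-2427, 1/10 = 10 points in pooled placebo.

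**Working it through.** The plan states no figure to reproduce here. Section 9.6 rests on clinical judgement, and its count is consistent: 5 × (4 + 2) = 30, with 5 × 4 = 20 active and 5 × 2 = 10 placebo. The check is how much a literal reading would cost.

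**Inputs**

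- Group sizes: 4 per dose, 20 and 10 pooled (sections 6.5 and 9.6).
- Pre-dose window: if enrolment means randomisation on Day -1 (section 3.3, Table 4), d is at most about 1 day.
- Background rate r: 0.002 to 0.01 AEs per subject-day. This is an assumption; the documents give no rate.

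**Step 1. Chance of a pre-dose event per subject.** q = 1 − exp(−r·d). For d = 1, q = 1 − exp(−0.002) = 0.0020, up to 1 − exp(−0.01) = 0.0100. Assignment is random and blinded, so q is the same in both arms.

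**Step 2. Effect on the comparison.** Let p0 and p1 be the chances of a post-dose event on placebo and ST-2427. If pre-dose events also count, a row shows 1 − (1 − q)(1 − p) in each arm, and the difference becomes (1 − q)(p1 − p0). The relative loss is q: 0.2% to 1%. For a single preferred term assumed to hold 10% to 30% of all events, r is multiplied by that share, and the loss is 0.02% to 0.3%.

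**Step 3. In percentage points.** Take p0 = 0.20 and p1 = 0.50 for illustration, a true difference of 30 points.

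| q | Difference shown | Loss |
|---|---|---|
| 0.002 | 0.998 × 30 = 29.94 | 0.06 points |
| 0.010 | 0.990 × 30 = 29.70 | 0.30 points |

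The smallest step the pooled table can take is 5 points on ST-2427 and 10 on placebo, so the expected loss is far below its resolution.

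**Step 4. How often it would happen.** The chance of at least one affected subject among n is 1 − exp(−n·r·d).

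- n = 4: 1 − exp(−0.008) = 0.8%, to 1 − exp(−0.04) = 3.9%.
- n = 20: 1 − exp(−0.04) = 3.9%, to 1 − exp(−0.2) = 18.1%.

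The expected number among the 20 is 20 × 0.002 = 0.04 to 20 × 0.01 = 0.2 subjects. A row changes only if that subject has no post-dose event in it.

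**Step 5. With an onset rule.** Section 8.4 supplies onset date and time. Dropping events that start before the infusion sets q = 0 and removes the whole effect.

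**The case for a change.** The strongest case for a change is that it would cost nothing, and that relying on custom is weaker than a written rule. It has three supports.

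**Start of collection.** The wording in section 8.4 could mean the whole screening period. With d = 28, q runs from 1 − exp(−0.056) = 5.4% to 1 − exp(−0.28) = 24.4%. But this rests on one unclear phrase. Section 8.2.1.1 starts recording at enrolment, and the adverse-event row of Table 4, badly aligned in the text available, does not clearly mark screening. These figures are also ceilings, since some people who fall ill in screening are never dosed.

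**Rate just before dosing.** Blood draws and standing tests take place within about an hour before the infusion and could cause symptoms, so a constant background rate may be too low. As a stress test, let 5% of subjects have a pre-dose event. The Step 3 example then shows 52.5% against 24.0%, a difference of 28.5 points instead of 30. At least one such subject would appear in a group of 4 with probability 1 − 0.95^4 = 18.5%, and among 20 with probability 1 − 0.95^20 = 64.2%. The loss of 1.5 points is still below the 5-point step, and these are events whose recorded time separates them most easily from post-dose ones. Section 8.4 also exempts clinically significant laboratory, blood pressure and pulse changes from AE reporting in most cases, which removes one likely source.

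**Worsening.** A full treatment-emergent rule must say how worsening of a pre-dose event is judged, and the protocol has both the intensity scale in section 8.4 and the FDA 2007 scale in section 9.1. That detail is open, but it matters only for a subject who has a pre-dose event that then worsens, a subset of an already rare group.

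What stands is the textual point: the definition is absent, and sections 8.2.1.1 and 8.4 describe the start of collection differently. The 25-point figure does not measure the defect. It is 1/4, the weight of any single subject in a group of four.

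**Conclusion.** The observation about the text is right, but it does not call for a change. Sections 8.2.1.1 and 8.4 say what is recorded; they do not say that every recorded event belongs in a table of treatment effects. The stated purpose of that table and the synopsis reference to treatment-emergent events both point to post-dose onset, and the data needed to apply this are already collected.

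If the rule were overlooked, the comparison would lose about 0.2% to 1% of its size, with no direction. This assumes 0.002 to 0.01 background events per subject-day and collection from Day -1. Only the broad reading of section 8.4 gives more, and that reading is poorly supported. The primary analysis is descriptive (section 9.6), so no error rate or sample size depends on it. In the text available, section 9.7 bases escalation on a review of safety and PK data, not on an AE percentage. The descriptive safety conclusion would be sound either way.

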9.2. Pharmacokinetic Analyses

PK modeling will be performed using compartmental methods. PK parameters including but not limited to C_{max}, T_{max}, Volume of distribution, Elimination half-life, and AUC after the ST-2427 infusion in the SAD.

Descriptive statistics will be used to summarize PK parameters, and ST-2427 concentrations in the urine by cohort.

In addition, exploratory analyses of the effects of some baseline characteristics (e.g., sex, body weight) on ST-2427 PK parameters may be undertaken.

9.3. **Analysis of ECGs**

ECGs will be collected during SAD as indicated in the Schedule of Events. Data from the ECGs will be used to determine cardiodynamic effects including concentration-QTc analysis. Details of this analysis will be given in a separate SAP and will include change-from-baseline ECG parameters (heart rate (HR), PR, QTcF and QRS), categorical outliers for HR, QTcF, PR and QRS and frequency of treatment emergent T- and U-wave abnormalities. For QTcF, the following categories will be used in the outlier analysis:

49

Page 48 of 62

Categorical analyses: number and proportion of subjects meeting the following corrected QT categories: >450 msec, >480 msec, and >500 msec,

9.4. Analysis Populations

The safety population will include all subjects who received at least one dose of study drug. Subjects will be analyzed as treated. The safety population will be used for all analyses of safety endpoints.

The PK population will include all subjects who received at least one dose of study drug, and who have sufficient data for evaluation of at least one PK parameter. Subjects will be analyzed as treated. Subjects randomized to placebo will not be included in the analysis.

9.5. Handling of Missing Data

Every effort will be made to query missing or spurious data prior to unblinding for DMC reviews and database lock.

Missing safety or PK data will not be imputed.

Deviations from the protocol will be recorded and assessed for potential to impact the trial outcomes.

9.6. Sample Size

Descriptive, non-inferential statistics are planned for the primary endpoint analyses. Based on clinical judgement, a sample size of 30 (20 randomized to ST-2427, and 10 randomized to placebo) is expected to be adequate to identify major treatment effects.

9.7. Data Monitoring Committee Reviews

A DMC consisting of the Principal Investigator, a medical representative from the Sponsor, and a PK expert, will be appointed for this study. Enrollment into Cohorts 2 through 5 will commence after all subjects in the prior cohort have completed the Follow-Up visit, and safety and PK data from all prior cohorts have been reviewed by the DMC, and no clinical concerns are identified. The DMC will additionally examine all available clinical and PK data to determine the dose of ST-2427 to be administered in the next cohort.

Page 49 of 62

The study will run to completion unless the Sponsor decides to terminate it earlier, e.g., following a recommendation from the DMC following review of all available PK and safety data.

10. DIRECT ACCESS TO SOURCE DATA/DOCUMENTS

10.1. Study Monitoring

Before an investigational site can enter a subject into the study, a representative of SiteOne Therapeutics, Inc. will:

- Determine the adequacy of the facilities
- Discuss with the Investigator(s) and other personnel their responsibilities with regard to
 protocol adherence, and the responsibilities of SiteOne Therapeutics, Inc. or its representatives.
 This will be documented in a Clinical Study Agreement between SiteOne Therapeutics, Inc.
 and the Investigator.

During the study, a monitor will have regular contacts with the investigational site, for the following:

- Provide information and support to the Investigator(s)
- Confirm that facilities remain acceptable
- Confirm that the investigational team is adhering to the protocol, that data are being accurately recorded in the CRFs, and that investigational product accountability checks are being performed
- Perform source data verification. This includes a comparison of the data in the CRFs with the patient's medical records at the hospital or practice, and other records relevant to the study. This will require direct access to all original records for each patient (e.g., clinic charts).
- Record and report any protocol deviations not previously sent to SiteOne Therapeutics, Inc...
- Confirm AEs and SAEs have been properly documented on CRFs and confirm any SAEs have been forwarded to SiteOne Therapeutics, Inc. and those SAEs that met criteria for reporting have been forwarded to the IRB.

The monitor will be available between visits if the Investigator(s) or other staff needs information or advice.

10.2. Audits and Inspections

Authorized representatives of SiteOne Therapeutics, Inc., a regulatory authority, an Independent Ethics Committee (IEC), or an Institutional Review Board (IRB) may visit the site to perform audits or inspections, including source data verification. The purpose of a SiteOne Therapeutics, Inc. audit

Page 51 of 62

or inspection is to systematically and independently examine all study-related activities and documents to determine whether these activities were conducted, and data were recorded, analyzed, and accurately reported according to the protocol, Good Clinical Practice (GCP) guidelines of the International Conference on Harmonization (ICH), and any applicable regulatory requirements. The Investigator should contact SiteOne Therapeutics, Inc. immediately if contacted by a regulatory agency about an inspection.

